5.3. Treatment Assignment Procedures

5.3.1. Randomization Procedures

Randomized treatment assignments will be generated by a statistician at ICON. Randomization will occur following admittance to the unit and confirmation of eligibility is confirmed.

This is a Phase 1 double-blinded, placebo-controlled trial that will randomize subjects within five dosing cohorts to either active or placebo.

Cohorts 1, 2, and 5

For cohorts 1, 2, and 5, the first two subjects will be randomized in a 1:1 fashion to active and placebo to ensure that one of the first two subjects receives active treatment and the other control. An alternate subject will be admitted to the unit for each two-subject group. If one of the first two subjects is not randomized for any reason, then the alternate subject will receive the next consecutive randomization number. The product assignment of the remaining subjects in each cohort will follow a 7:1 randomization of active to placebo, respectively. The randomization list will be generated by the unblinded study biostatistician and uploaded to IRT

system by vendor (4G Clinical). Upon confirming eligibility of subjects, site research personnel will randomize subjects then the unblinded study pharmacist will be notified of treatment allocation via system-generated email.

Cohort 3 and 4

Subjects in cohort 3 and 4 will be randomized in a 4:1 ratio of active to placebo. The randomization list will be generated by the unblinded study biostatistician and uploaded to IRT system by vendor (4G Clinical). Upon confirming eligibility of subjects, site research personnel will randomize subjects then the unblinded study pharmacist will be notified of treatment allocation via system-generated email.

5.3.2. Masking Procedures

The study staff participating in the administration of study product and assessment of the subjects will not be aware of the contents of the vial. The ADM03820 and placebo will look identical, so the study staff and the subject will not be able to determine whether placebo or ADM03820 is being injected.

The Investigator may unblind a subject's treatment assignment only in the case of an emergency or SAE, when knowledge of the study treatment is essential to the appropriate clinical management or welfare of the subject. Whenever possible, the Investigator should first discuss the options with the ICON GPHS Medical Monitor and the RGS ML or appropriately designated RGS personnel before unblinding the subject's treatment assignment. If this is impractical, the Investigator must notify the ICON GPHS Medical Monitor and RGS as soon as possible but without revealing the subject's treatment assignment. The date and reason for unblinding must be recorded on the SAE form.

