Since this is a first-in-human study, administration of the study products to subjects in cohorts 1, 2 and 5 will occur to allow careful observation of individuals for adverse events. Two sentinel subjects within each cohort will be admitted and administered a dose on Day 1 to remain in the clinic until Day 2. The randomization scheme will be designed to ensure that one subject will receive ADM03820 and the other will receive placebo. The IM dosing of the remaining subjects within cohorts 1, 2, and 5 will not be initiated until at least 48 hours have passed and no adverse events have occurred that meet halting criteria, and no safety signals have occurred that in the opinion of the investigator warrant further investigation. The remaining subjects within each specific cohort will be dosed at least four hours apart until all subjects in the cohort have been dosed. An alternate subject will be admitted to the unit for each two-subject group. Dose escalation will not occur until safety data through Day 8 is reviewed by the SRC.

Cohort 1 (150 mg IM injection) will be dosed first. Two sentinel subjects (one ADM03820 and one placebo) will each be administered a single 3 mL IM injection. The dosing of the next subjects within Cohort 1 will not be initiated until at least 48 hours have passed and no adverse events have occurred that meet halting criteria and no safety signals have occurred that in the

opinion of the investigator warrant further investigation. The remaining subjects in the cohort will be dosed at least four hours apart until all subjects in the cohort have been dosed.

Dose escalation to Cohort 2 will not occur until safety data through day 8 for Cohort 1 is reviewed by the SRC. Objective dose escalation criteria and safety evaluations will be utilized.

In Cohort 2 (300 mg IM injection), two sentinel subjects (one ADM03820 and one placebo) will each be administered two 3 mL IM injections. Dosing for the remaining subjects in Cohort 2 will be initiated after at least 48 hours have passed and no adverse events have occurred that meet halting criteria and no safety signals have occurred that in the opinion of the investigator warrant further investigation. The remaining subjects in the cohort will be dosed at least four hours apart until all subjects in the cohort have been dosed.

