6. STUDY PRODUCTS

6.1. Description of Study Products

ADM03820 is a 1:1 mixture of two human IgG1 non-competitive anti-SARS-CoV-2 antibodies formulated as 50 mg/mL or 100 mg/mL strength solutions in a 2 mL vial for IM administration. The drug product is a clear to opalescent, slightly colored, sterile aqueous solution at Ph 6. ADM03820 is formulated in 141 Mm L-arginine, 10 Mm sodium succinate buffer, with 0.25% v/v Polysorbate 80 and is filled as 1.2 mL in a 2 mL vial (50 mg/mL) or 1.7 mL in a 2 mL vial (100 mg/mL).

Placebo is 0.9% Sodium Chloride Injection, USP is a sterile, nonpyrogenic, isotonic solution of sodium chloride and water for injection.

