6.3. Formulation, Packaging, and Labeling

ADM03820

ADM03820 is a 1:1 mixture of two human IgG1 non-competitive anti-SARS-CoV-2 antibodies formulated as 50 mg/mL or 100 mg/mL strength solutions in a 2 mL vial for IM administration. The drug product is a clear to opalescent, slightly colored, sterile aqueous solution at Ph 6. ADM03820 is formulated in 141 Mm L-arginine, 10 Mm sodium succinate buffer, with 0.25% v/v Polysorbate 80 and is filled as 1.2 mL in a 2 mL vial (50 mg/mL) or 1.7 mL in a 2 mL vial (100 mg/mL).

The drug product will be supplied in 2-mL, pyrogen-free, Type 1 glass vials fitted with Tefloncoated butyl rubber stoppers and flip-up aluminum seals.

ADM03820 will be administered by intramuscular (IM) injection as follows: 150 mg (Cohort 1 as 1 x 3 mL IM injection) or 300 mg (Cohorts 2 and 3 as 2 x 3 mL IM injections or Cohort 4 as 1 x 3mL IM injection) or 600 mg (Cohort 5 as 2 x 3 mL IM injections).

Placebo (Normal Saline, 0.9% Sodium Chloride, USP)

0.9% Sodium Chloride Injection, USP is a sterile, nonpyrogenic, isotonic solution of sodium chloride and water for injection. Each mL contains sodium chloride 9 mg and contains no preservatives, bacteriostatic, antimicrobial agent, or added buffer. The solution is clear in appearance with a Ph range of 4.5 to 7.0.

Placebo will be administered by intramuscular (IM) injection as follows: 150 mg (Cohort 1 as 1 x 3 mL IM injection) or 300 mg (Cohorts 2 and 3 as 2 x 3 mL IM injections or Cohort 4 as 1 x 3mL IM injection) or 600 mg (Cohort 5 as 2 x 3 mL IM injections).

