6.5. Dosage, Preparation and Administration

The unblinded site Research Pharmacist will prepare the study drug on the same day as administration. Prior to using any of the parenteral products, inspect for discoloration or particulate matter before use. Any product that fails inspection should be quarantined at 2-8°C for inspection by the Sponsor. Preparation of the product will be performed using aseptic technique under a sterile environment (e.g., Biologic Safety Cabinet or laminar flow hood). Based on the subject assigned cohort randomization, the appropriate ADM03820 dose will be calculated, and the appropriate number of vials will be removed from storage to prepare for dosing. Vials containing ADM03820 should not be vigorously shaken. Any unused portion left in the vial should be retained for study product accountability as per Section 6.6. The placebo will be normal saline, 0.9% sodium chloride.

The subjects will be admitted to the Phase 1 unit the day of the planned dosing. Verification that the subject still meets all inclusion criteria and does not have any exclusion criteria must be made prior to randomization. The unblinded site Research Pharmacist will prepare the dose as described. Administration of the IM dose of ADM03820 or placebo should be injected into the gluteus medius (see Appendix C) and must be completed within 30 minutes of preparation.

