APPENDIX C: INTRAMUSCULAR (IM) ADMINISTRATION

Cohorts 1-3 Only: IP is administered as one 3mL (150mg dose) or two 3mL (300mg dose) IM injection(s) within 1 hour of thawing.

Cohort 4 Only: IP is administered as one 3mL (300mg dose) IM injection within 30 minutes of removing from refrigerator.

Cohort 5 Only: IP is administered as two 3mL (600mg dose) IM injection within 30 minutes of removing from refrigerator.

Instruct subject to lay prone (on abdomen) with toes pointing inward and heels apart (to relax gluteal muscles). Visually divide the buttock in half from top to bottom and then in half from side to side. The injection should be given in the upper outer quarter to avoid the sciatic nerve and gluteal artery. Intramuscular (IM) injections are administered into the gluteus medius muscle of the buttocks using a 1 ½ inch 20 or 22 gauge needle. Inject entire contents of syringe and remove needle. Do not rub the injected area. Gentle pressure is allowable if bleeding is noted.

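### The staff blind rests on active and placebo looking the same, but the protocol describes them differently and nothing in the protocol or SAP masks the filled syringe

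*Protocol*

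**What the plan says.** Protocol 5.3.2 names two groups of staff to be kept blind: those who give the product and those who assess subjects. It says they will not know what the vial contains, and then gives the mechanism: "The ADM03820 and placebo will look identical, so the study staff and the subject will not be able to determine" which of the two is injected.

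The product sections describe the two solutions in different terms. For the active, 6.1 says "The drug product is a clear to opalescent, slightly colored, sterile aqueous solution", and 6.3 repeats it. The placebo is 0.9% saline supplied by the site (6.2), and 6.3 says of it: "The solution is clear in appearance with a Ph range of 4.5 to 7.0". Section 6.1 gives no appearance for the saline.

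Under 5.3.1 the allocation is emailed to an unblinded pharmacist. Section 6.5 then says: "The unblinded site Research Pharmacist will prepare the dose as described". The same section asks for a visual check of parenteral products: "inspect for discoloration or particulate matter before use". Appendix C instructs the person injecting: "Inject entire contents of syringe and remove needle".

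**The concern.** If the two solutions can be told apart in the syringe, some judgements could be made by staff who know or suspect the assignment.

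- **Adverse event reporting, severity and relatedness.** The investigator grades severity and judges relatedness (Protocol 9.2.1 and 9.2.2). A study physician should be present at dosing (8.2), so an assessor could plausibly see the syringe.
- **The 48-hour sentinel gate.** Dosing of the rest of Cohorts 1, 2 and 5 depends partly on investigator opinion that "no safety signals have occurred that in the opinion of the investigator warrant further investigation" (Section 4).
- **The halting criterion for a related serious event.** One serious adverse event judged possibly or definitely related stops dosing for review (9.5.1).

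The sentinel design makes recognition more informative. Section 5.3.1 pairs the first two subjects "to ensure that one of the first two subjects receives active treatment and the other control", so identifying one member of a pair identifies the other.

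**Working it through.** No figure in the plan bears on this point, so the check compares the texts.

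1. **What must be true for 5.3.2 to work.** Identical appearance is the only stated reason that staff cannot tell the products apart. If appearance differs, that reason fails and something else must carry the blind.

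2. **Do the descriptions match?**
   - Clarity: the active runs from clear to opalescent and the saline is clear. The two agree at the clear end of the active's range and differ at the opalescent end.
   - Color: the active is slightly colored. No color is given for the saline, so this attribute has no counterpart.
   - Composition: the active contains arginine, succinate buffer and polysorbate 80 (6.1), whereas the placebo is plain unbuffered saline (6.3). It is not a matched vehicle, so similar appearance cannot be inferred from the formulation.

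3. **What the unblinded pharmacist covers.** Receiving the allocation and preparing the dose (5.3.1, 6.5) keeps the randomization list and the vial away from blinded staff. The injector still handles a filled syringe (Appendix C). The first sentence of 5.3.2 speaks of the vial, not the syringe.

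4. **Is the syringe masked anywhere?** Protocol 5.3.1, 5.3.2, 6.5, the dosing visit in 8.2, Appendix C and the SAP mention no opaque syringe, sleeve, overlay or separate unblinded injector. The protocol sends the reader to the Manual of Procedures for other matters (7.2, 7.5.3, 7.6.6), but not in 5.3.2 or 6.5.

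5. **Who is affected.** Appendix C has the subject lie prone for a gluteal injection, so the subject is unlikely to see the syringe. The point concerns the staff blind.

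6. **Which outputs depend on the blind.** Reporting, grading and causality of adverse events do. Laboratory values and the PK, microneutralization and anti-drug antibody assays depend on it very little.

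The descriptions do not support the stated mechanism, and no second mechanism is written down.

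**The case against.** The strongest reply is that this is a mismatch of wording. The active may be clear, the saline is clear, and a slight color may not show in a 3 mL syringe. Section 5.3.2 also commits to staff being unable to tell the products apart. Operational detail is placed in a Manual of Procedures, and departures from that manual count as deviations (15.6), so a masking step may already exist there.

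Much of this stands. A reader might infer that the trial was in effect open to site staff. The documents do not support that: they show neither a visible difference nor any unblinded person. A reader might also infer that no masking took place. Without the manual or any pharmacy manual, the most that can be said is that none is stated in the protocol or SAP.

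The consequences are limited too. The SAP's safety analysis section plans no tests on safety endpoints, so no formal safety comparison is at risk. The sentinel gate also requires that no event meets the halting criteria. Escalation needs unanimous agreement of the Safety Review Committee (9.5.3), two of whose three members are the sponsor's medical lead and the contract research organization's medical monitor (9.6.4). The Independent Safety Monitor reviews serious events (9.6.1).

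The reply does not remove the conflict. The reason given in 5.3.2 still disagrees with 6.1 and 6.3, and a commitment to a blind is not a method for keeping it.

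**Conclusion.** The staff blind is not assured as written. This is more than missing detail, because the one mechanism the protocol names conflicts with its own product descriptions, and the staff it is meant to protect include those who judge adverse events.

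The consequence is conditional on the difference being visible in a filled syringe to someone who makes those judgements. The documents do not settle that condition, and the size and direction of any bias cannot be computed from them. A reader might infer that the primary safety results are biased. That goes too far. Severity and relatedness are breakdowns of the adverse event summaries, not part of the primary endpoints in 3.2.1. The occurrence of adverse events is a primary endpoint, and only its reporting could be influenced. Laboratory changes, also in the primary set, depend little on the blind.

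It is worth correcting because it is cheap to correct and because readers of the safety tables will rely on the double-blind label.

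**What to change.** 1. In Protocol 5.3.2, reconcile the statement about appearance with the descriptions in 6.1 and 6.3, or remove it.
2. In 5.3.2 and 6.5, state that for every dose still to be given the unblinded pharmacist dispenses active and placebo in syringes masked by an opaque sleeve or overlay. The plunger must stay visible, because the injector has to give the full contents. If the Manual of Procedures or a pharmacy manual already requires masking, a cross-reference is enough.
3. For doses already given without masking, state this as a limitation in the clinical study report. The documents do not say how many doses have been given, and a sleeve helps only future ones.

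The cost is a few sentences and one sleeve per remaining injection, applied by the existing pharmacist, with no added visits or staff. If no planned dose had yet been given, and assuming one syringe per injection in 6.3, the ceiling before replacements would be 2 cohorts × 10 subjects × 1 injection (Cohorts 1 and 4) + 3 × 10 × 2 (Cohorts 2, 3 and 5) = 20 + 60 = 80 sleeves. The downside is that blinded staff cannot inspect the contents at the bedside, so visual inspection stays with the pharmacist at preparation.

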5.3.3. Reasons for Withdrawal

A subject may withdraw from the study at any time for any reason, without any consequence.

A study subject will be discontinued from participation in the study if any of the following reasons occur prior to dosing:

- Development of any exclusion criteria;
- Request by the subject to terminate participation;
- Requirement for prohibited concomitant medication or treatment;

A subject may be removed from the study for the following reasons post dosing; however, whenever possible the subject should be followed for safety per protocol:

- Failure to adhere to the protocol requirements
- Lost to follow-up;
- Request of primary care provider;

- At the request of the Institutional Review Board (IRB)/Ethics committee, Food and Drug Administration (FDA), or DOD;
- The subject's well-being based on the opinion of the investigator;
- The occurrence of a Serious Adverse Event (SAE) or (AE warranting withdrawal).

5.3.4. Handling of Withdrawals

Subjects who are withdrawn prior to dosing must be replaced.

Following dosing, one subject per cohort may withdraw prior to the completion of Visit 11 (day 60) or was noncompliant with all PK draws through Visit 6 (day 4) without being replaced.

If 4 or more subjects withdraw, are lost to follow up or terminate prior to Day 8 within a cohort, at least one of those subjects need to be replaced to ensure that data for at least 7 subjects are available for review.

If 4 or more subjects withdraw, are lost to follow up or terminate on or after Day 8 but prior to Day 60 or are not compliant with all PK draws through Day 15 within a cohort, they should be replaced.

If more than 4 subjects withdraw, are lost to follow up or terminate following the Day 8 SRC review of safety data within a cohort, the site will attempt to replace those subjects in that dose group at the time of the next planned cohort.

All replaced subjects will be assigned to the same treatment assignment as the subject they are replacing. This will be documented in the source documents and eCRFs.

5.3.5. Lost to Follow-up

In the case of subjects who fail to appear for a follow-up assessment, extensive effort (i.e., three documented contact attempts via phone calls, e-mail, etc., made on separate occasions and followed by a certified letter) will be made to locate or recall them, or at least to determine their health status. These efforts will be documented in the subjects' records.

5.3.6. Termination of Study

Although the study Sponsor has every intention of completing the study, it reserves the right to terminate the study at any time for clinical or administrative reasons.

6. STUDY PRODUCTS

6.1. Description of Study Products

ADM03820 is a 1:1 mixture of two human IgG1 non-competitive anti-SARS-CoV-2 antibodies formulated as 50 mg/mL or 100 mg/mL strength solutions in a 2 mL vial for IM administration. The drug product is a clear to opalescent, slightly colored, sterile aqueous solution at Ph 6. ADM03820 is formulated in 141 Mm L-arginine, 10 Mm sodium succinate buffer, with 0.25% v/v Polysorbate 80 and is filled as 1.2 mL in a 2 mL vial (50 mg/mL) or 1.7 mL in a 2 mL vial (100 mg/mL).

Placebo is 0.9% Sodium Chloride Injection, USP is a sterile, nonpyrogenic, isotonic solution of sodium chloride and water for injection.

6.2. Acquisition

The ADM03820 will be supplied by Resilience Government Services (Previously Ology Bioservices, Inc.) Study product will be shipped to the site.

The normal saline for injection will be supplied by the study site.

6.3. Formulation, Packaging, and Labeling

ADM03820

ADM03820 is a 1:1 mixture of two human IgG1 non-competitive anti-SARS-CoV-2 antibodies formulated as 50 mg/mL or 100 mg/mL strength solutions in a 2 mL vial for IM administration. The drug product is a clear to opalescent, slightly colored, sterile aqueous solution at Ph 6. ADM03820 is formulated in 141 Mm L-arginine, 10 Mm sodium succinate buffer, with 0.25% v/v Polysorbate 80 and is filled as 1.2 mL in a 2 mL vial (50 mg/mL) or 1.7 mL in a 2 mL vial (100 mg/mL).

The drug product will be supplied in 2-mL, pyrogen-free, Type 1 glass vials fitted with Tefloncoated butyl rubber stoppers and flip-up aluminum seals.

ADM03820 will be administered by intramuscular (IM) injection as follows: 150 mg (Cohort 1 as 1 x 3 mL IM injection) or 300 mg (Cohorts 2 and 3 as 2 x 3 mL IM injections or Cohort 4 as 1 x 3mL IM injection) or 600 mg (Cohort 5 as 2 x 3 mL IM injections).

Placebo (Normal Saline, 0.9% Sodium Chloride, USP)

0.9% Sodium Chloride Injection, USP is a sterile, nonpyrogenic, isotonic solution of sodium chloride and water for injection. Each mL contains sodium chloride 9 mg and contains no preservatives, bacteriostatic, antimicrobial agent, or added buffer. The solution is clear in appearance with a Ph range of 4.5 to 7.0.

Placebo will be administered by intramuscular (IM) injection as follows: 150 mg (Cohort 1 as 1 x 3 mL IM injection) or 300 mg (Cohorts 2 and 3 as 2 x 3 mL IM injections or Cohort 4 as 1 x 3mL IM injection) or 600 mg (Cohort 5 as 2 x 3 mL IM injections).

6.4. Product Storage and Stability

ADM03820

Cohorts 1-3

ADM03820 drug product (50mg/mL) will be shipped frozen and should be stored at -90°C to -70°C until time of preparation. If a vial is removed from the freezer it must be used within 1 hour of thawing. If not used, it must be quarantined and maintained for study product accountability as per Section 6.6. ADM03820 should be protected from direct sunlight.

ADM03820 is not light sensitive under normal shipping and storage conditions. Avoid vigorous shaking or agitation.

Cohorts 4 and 5 Only

ADM03820 (100mg/mL) drug product will be shipped and should be stored at 2°C to 8°C until time of preparation. If a vial is removed from the refrigerator it must be used within 30 minutes. If not used, it must be quarantined and maintained for study product accountability as per Section 10.5. ADM03820 should be protected from direct sunlight. ADM03820 is not light sensitive under normal shipping and storage conditions. Avoid vigorous shaking or agitation.

Placebo (Normal Saline, 0.9% Sodium Chloride, USP)

Store at 20°C to 25°C (68°F to 77°F) [See USP Controlled Room Temperature; excursions between 15°C and 30°C (59°F and 86°F) are permitted]. Protect from freezing.

